We hypothesize that preterm infants supplemented with early physiologic doses of L-carnitine while on parenteral nutrition will have improved short-term growth parameters and significantly higher neurobehavioral scores when compared with control infants.

Primary Aims:

To determine whether carnitine supplementation is associated with:

- 1. Decreased percent weight loss within the first two weeks of life and decreased length of time to regain birthweight.
- 2. Improved performance on the NICU Network Neurobehavioral Scale (NNNS) at 40 weeks postmenstrual age (+/- 2 weeks).

Secondary Aims:

To determine whether carnitine supplementation is associated with:

- 1. Increased rate of growth of head circumference within the first month of life and increased food efficiency (weight gain/calorie intake) during the supplementation period.
- 2. Normalization of the serum carnitine profile at two weeks of life, compared with infants born at a post-menstrual age 2 weeks later.
- 3. Enhanced brain maturation as measured by amplitude-integrated EEG (aEEG) measurements obtained during the hospital course
- 4. Fewer abnormal findings, better brain growth, white matter development and brain metabolism on brain magnetic resonance imaging (MRI) at 36-40 weeks' corrected age (prior to hospital discharge)

Because of the potential for systemic effects of L-carnitine supplementation, we will also monitor those variables which showed significant difference in our prior study: rates of proven infection, hearing screen failure and PDA ligation.

Primary Outcomes:

- 1. Length of time to regain birthweight,
- 2. Percent weight loss in the first two weeks of life,
- 3. Neurodevelopmental scores on the NICU Network Neurobehavioral Scale (NNNS) at 40 weeks post-menstrual age (+/- 2 weeks)

Methods/Design:

This is a prospective, randomized controlled clinical trial involving infants with gestational age (GA) <32 wks who are born at either the Jack D. Weiler Hospital or the Wakefield Division of Montefiore and admitted to theirNeonatal Intensive Care Unit. Informed consent will be obtained from the parents of eligible patients as early as possible within 72 hours of birth. Infants whose parents have signed an informed consent form will be randomized to receive either carnitine supplementation (50 µmol/kg/day) versus placebo within 72-96 hours of birth.

Inclusion criteria:

- Infants born <32weeks' gestation
- Exclusion criteria:
 - Presence of

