- 1. Patient demographics: date of birth, birth weight, gestational age as determined by best obstetric estimate or Ballard score, SGA or LGA status, Apgar scores, birth history, delivery room management, gender, ethnicity.
- 2. Maternal characteristics: maternal age, maternal language, ethnicity, presence of prenatal care, type of insurance coverage, maternal educational status, presence of maternal depression, teratogen exposure (alcohol, tobacco or illicit drug use during pregnancy), antenatal steroid use, hypertension/pre-ecclampsia, gestational diabetes/Type I or II diabetes, and maternal infections.
- 3. Management of fluid and nutrition: daily fluid intake and urine output, glucose infusion rate, total caloric intake, total protein intake, and food efficiency (weight gain divided by caloric intake) while on study supplement.
- 4. Hospital course:
 - a. Growth parameters: weight, length and head circumference at birth, daily weight until birthweight regained and then weekly, weekly length, and head circumference two times per week for four weeks)
 - b. Cardiovascular: need for vasopressors, presence of PDA (including medical or surgical treatment; platelet count and mean fluid intake at time of treatment)
 - c. Gastrointestinal: feeding intolerance, NEC, presence of gastrointestinal reflux,
 - Neurological: results of aEEG readings, results of head ultrasounds including presence of germinal matrix/intraventricular hemorrhage and periventricular leukomalacia, cranial MRI results
 - e. Opthalmological: grade of retinopathy of prematurity and treatment or ophthalmologic diagnosis,
 - f. Hematologic: transfusion history including dates
 - g. Infectious disease: presence of concurrent presumed and proven infection,
 - h. Other: performance of any surgical procedures, duration of intravenous access, use of medications, and hearing screen results (OAE and/or ABR) with observed thresholds of hearing frequencies.
 - i. Clinical Risk Index for Babies (CRIB) scores will be calculated for each infant.
 - j. We will also monitor for possible short-term side effects.
- 5. Discharge information: weight, length, head circumference, and diagnoses at time of discharge, routinely-ordered discharge brain MRI findings
- 6. Neurodevelopmental assessment:

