 - a. Study patients will be followed at 40 weeks PMA (+/- 2 weeks) to assess neurodevelopmental outcomes among survivors (including incidence of cerebral palsy, neurobehavioral delay, blindness and deafness). Patient information such as weight, length, head circumference, and inter-current illness will be recorded. Infants will be tested using the NICU Network Neurobehavioral Scale, and their scores recorded.
 - Study patients will be followed at 18-24 months corrected age to assess neurodevelopmental outcomes. During this follow-up visit, we will administer the following:
 - i. Bayley Scales of Infant and Toddler Development, Third Edition (BSID-III)
 - ii. Modified Checklist for Autism in Toddlers (M-CHAT)
 - iii. Child Behavior Checklist (CBCL)

Amplitude-integrated EEG measurements (aEEG)

It has previously been reported that background aEEG activity is concordant with the neurological examination and with background patterns on full-scale EEG.^{43,44} Furthermore, in preterm infants, aEEG appears to have a predictive value for developmental outcomes at 3 years of age.⁴⁵ We will, therefore, use aEEG recordings for neurophysiological assessments in our study population. Sedation is not required for this procedure.

We will perform 3-hour aEEG recordings within 2-3 days of initiation of carnitine or placebo supplementation and then at the following PMA: 28 weeks', 32 weeks', 36 weeks', and at 40 weeks' PMA if infant is still admitted to the NICU. aEEG readings will be recorded from the surface of the brain using surface disc electrodes and a Cerebral Function Monitor (CFM) System (Olympic Brainz Monitor; Natus Medical Inc., San Carlos, CA). The Brainz monitor is a bedside brain monitor designed for continuous use in the NICU environment. With its 2-channel capability, this system offers clinicians the ability to monitor brain function at the bedside displaying both real time EEG activity and a time-compressed trend of EEG called amplitude integrated EEG (aEEG) from both cerebral hemispheres. The EEG recordings are stored as downloadable digital files for offline analysis and archiving. The quality of the recording will be monitored by continuous impedance tracing. The tracings will be assessed for both quantitative and qualitative characteristics observed in the whole tracing. We will assess the following: (1) continuity, (2) sleep-wake cycling, (3) voltage and span or bandwidth of the signals, and (4) presence or absence of seizure activity.

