We will assess neurodevelopmental outcomes at 18-24 months corrected age using the Bayley Scales of Infant and Toddler Development, Third Edition (BSID-III). The BSID-III is a validated instrument used for assessing the development of Cognitive, Language (Receptive and Expressive), Motor (Fine and Gross), Social-Emotional and Adaptive skills in infants and toddlers. This normative assessment yields scaled scores, composite scores, percentile ranks, and developmental age equivalents, all of which provide important information about a child's level of functioning relative to his or her same-age peers. While Cognitive, Language and Motor skills are assessed through direct interaction with the child, Social-Emotional and Adaptive skills are obtained from parent report. Because the BSID-III is commonly used for identifying children who are in need of early intervention due to developmental delays, this instrument will be sensitive to detecting the types of developmental issues we often see in very young children born preterm. Additionally, at the follow-up visit at 18-24 months corrected age, we will administer two parental questionnaires: the Modified Checklist for Autism in Toddlers (M-CHAT) and the Child Behavior Checklist (CBCL). M-CHAT is a parent-report checklist developed to screen children for early signs of autistic features. The CBCL is a standardized, well-validated parent-report questionnaire developed to assess various maladaptive behavioral and emotional problems in young children.

Record confidentiality: Records relating to the study will be kept in a secure location, to which only study personnel will have access. Records will be kept in a locked file cabinet in the neonatology offices and in a password-protected computer.

Statistical Analyses:

Statistical analysis will be performed with the assistance of a statistician.

Sample size:

We plan to recruit a total of 150 infants for our study over approximately 36months' time. This number is based upon an expected attrition of approximately 50 infants over the course of the study and a desired sample size of 100 infants. The inclusion of 100 infants in our study (50 in each study arm) will allow us to detect a moderate difference in our primary outcomes at a significance level of 0.05 with a power of 0.8. (0.5 SD; α = .05; power = .80).

Primary Outcomes	Mean	Standard Deviation	0.5 x Standard Deviation
Percent weight loss*	10.8%	6.2	3.1
Time to regain	11.3 days	4.3	2.2
birthweight*			

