The effect of L-carnitine supplementation on outcome measures in enrolled infants will be examined for significance by comparing the two groups using unpaired data analysis with the assistance of a statistician. Continuous data (percent weight loss, time to regain birthweight, NNNS score, BSID-III scores) will be compared between the "placebo" and the "carnitine supplemented" groups by unpaired student t-test (a 2 tailed P value <0.05 will be considered to indicate statistical significance) or Wilcoxon's rank sum test for non-parametric parameters. Unmatched nominal data will be compared using Fisher's Exact Test or Chi-square test as required (e.g.: presence or absence of normalization of the carnitine profile; or presence or absence of pathological findings on the discharge MRI). Logistic regression models will be used to adjust for potentially confounding factors including gestational age, birth weight, race, gender, Apgar scores.

Risks and Discomforts:

A brief description of the risks and discomforts associated with this study is included in the protocol consent form and will be discussed in detail with each family at the time of study enrollment.

Carnitine is routinely administered with parenteral nutrition in approximately one-third of the neonatal intensive care units in the United States, although not in the Jack D. Weiler Hospital or Montefiore North Division NICU's. Carnitine is FDA-approved, and there have been no reports of severe toxicity from

overdose. Data available from the adult literature reports side effects of mild gastrointestinal symptoms such as gastritis, vomiting, diarrhea or abdominal cramping; body odor; and seizures, in patients with or without a known seizure disorder. These side effects are dose-dependent and might be avoided by slow consumption of the solution or greater dilution. One investigator reported transient elevation of triglycerides and increased platelet aggregation in uremic patients with severe renal insufficiency who received high doses of carnitine supplementation.⁵²

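### The NNNS scores may be taken anywhere from 38 to 42 weeks PMA but are compared with no adjustment for age at examination or randomisation stratum, which gives away precision

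*Combined protocol and SAP*

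**What the plan says.** Under Primary Outcomes, the third item is "Neurodevelopmental scores on the NICU Network Neurobehavioral Scale (NNNS) at 40 weeks post-menstrual age (+/- 2 weeks"). The Timeline of Assessments repeats the window, and so does the neurodevelopmental item under Data collection: "Study patients will be followed at 40 weeks PMA (+/- 2 weeks) to assess neurodevelopmental outcomes among survivors". That item lists what is recorded at the visit (growth measures, illness, scores) but does not name the date of the examination or the infant's PMA on that day.

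Under Outcome Measures, NNNS scores are to be compared "by unpaired student t-test (a 2 tailed P value <0.05 will be considered to indicate statistical significance"), or by a rank sum test where a parametric test does not fit. The only adjusted analysis follows: "Logistic regression models will be used to adjust for potentially confounding factors including gestational age, birth weight, race, gender, Apgar scores". The gestational age in that list is a characteristic at birth. Data collection places it with the patient demographics, as "gestational age as determined by best obstetric estimate or Ballard score".

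The Randomization section stratifies into three gestational-age bands plus an SGA stratum, on the ground that these variables affect the outcomes. The analysis text does not carry the strata forward.

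**The concern.** The Neurobehavioral Assessment section describes the NNNS as scoring muscle tone, primitive reflexes, central nervous system integrity and behavioural responses. The protocol treats these weeks as a period of brain maturation: it schedules aEEG at set postmenstrual ages and has a secondary aim on maturation. If scores move with age between 38 and 42 weeks, the spread of examination ages goes into the error term of a primary outcome. An adjusted model could remove it.

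The planned adjustment cannot. A logistic model needs a binary outcome, and no cut-point for NNNS scores is given. Its covariates describe the infant at birth, not at testing. Normed scores are said to exist, but there is no stated plan to use age-normed ones. As written, this primary outcome has no usable adjusted analysis, and maturity at birth is controlled by design while maturity at testing is left free. What is at stake is power in a trial with little to spare.

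**Working it through.** **1. The plan's own figure.** The Sample size section gives "The inclusion of 100 infants in our study (50 in each study arm") and "0.5 SD; α = .05; power = .80". With d = 0.5 and n = 50 per arm, the noncentrality is d·√(n/2) = 0.5 × 5 = 2.5 on 98 degrees of freedom.

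- One-sided 0.05: power 0.799. This reproduces the stated 0.80.
- Two-sided 0.05, the level declared under Outcome Measures: power 0.697, with 64 per arm needed for 80%.

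The baseline below is therefore 0.70. The gap between 0.80 and 0.70 comes from sidedness and is a separate matter.

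**2. Spread of examination age (s), not given in the documents.** Two assumptions are used:

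- even over 38–42 weeks: s = 4/√12 = 1.155 weeks;
- clustered near 40 weeks: s = 0.6 weeks.

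**3. Weekly change in score (b, in SD per week), not given in the documents.** The assumed range is 0.1 to 0.5. Age then contributes variance v = (b·s)².

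The NNNS planning SDs in the Power Calculation table come from a cited normative sample of healthy infants, whose spread of age at testing is not stated. So there are two cases:

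- Case A, the planning SD excludes age spread: the unadjusted SD is √(1+v), and adjustment restores it to 1.
- Case B, the planning SD includes it: the unadjusted SD is 1, and adjustment lowers it to √(1−v).

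Exact t power, two-sided 0.05, 50 per arm, even spread:

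| b | v | A: unadjusted SD | A: unadjusted power (adjusted 0.697) | A: n per arm for 80%, unadjusted | B: adjusted SD | B: adjusted power (unadjusted 0.697) |
|---|---|---|---|---|---|---|
| 0.1 | 0.013 | 1.007 | 0.691 | 65 | 0.993 | 0.703 |
| 0.3 | 0.120 | 1.058 | 0.648 | 72 | 0.938 | 0.751 |
| 0.5 | 0.333 | 1.155 | 0.573 | 85 | 0.816 | 0.858 |

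At b = 0.2 with an even spread, v = 0.053. Power is 0.67 unadjusted in case A and 0.72 adjusted in case B, so the difference is between 2 and 3 points.

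Clustered, with b = 0.4: v = (0.4 × 0.6)² = 0.058. Power is 0.67 unadjusted in case A and 0.72 adjusted in case B, again under 3 points from 0.697.

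The few degrees of freedom spent on covariates are ignored. Any gain from adjusting for the strata is not counted, because the documents give no basis for it.

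**4. Chance imbalance in examination age.** With an even spread, the difference in mean age between arms has SD 1.155 × √(2/50) = 0.231 weeks. At b = 0.1 / 0.3 / 0.5 this moves the result by 0.023 / 0.069 / 0.115 SD. The standard error of the treatment difference is √(2/50) = 0.2 SD before any age variance, and the unadjusted test's own standard error includes that variance. A half-week imbalance would be 0.5/0.231 ≈ 2.2 SDs, roughly a 3% event. With s = 0.6 it would be 0.5/0.12 ≈ 4 SDs.

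**The case against.** A reader might infer that the wide window biases the comparison. The documents do not support this. Infants are randomised in blocks of four within strata, and clinicians and nurses are blinded, so examination age is balanced in expectation. A chance imbalance is random error, which the standard error already covers. Systematic bias would need carnitine, or differential loss, to change when infants are seen. The plan does foresee "expected attrition of approximately 50 infants over the course of the study", out of 150 recruited, so differential loss cannot be excluded, but nothing shows that it would act through visit timing. This objection stands.

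The size can also be challenged. Both the slope and the spread are assumed. The examination belongs to a routine term-equivalent visit, and the infant timeline places it at the due date, so clustering near 40 weeks is plausible. The lowest figure, 0.57, needs the steepest slope, a flat spread and planning SDs free of age variation, all together. This also stands, and it limits the claim to a range.

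The covariate list is open-ended, so age at examination is not excluded. That is true, but an unnamed covariate is not pre-specified, and the model type would still not fit.

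Finally, a linear model is a poor choice for some scores. The Power Calculation table gives Hypertonicity 0.07 (SD 0.26), Hypotonicity 0.55 (0.76) and Handling 0.27 (0.27), which suggests skew and values near the floor. The rank sum option exists for such scores and should not be lost.

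**Conclusion.** The point holds as a loss of precision that is cheap to avoid. The four-week window, the unadjusted comparison and the ill-fitting logistic model are facts of the text. The loss is small (under about 3 power points) at slopes up to 0.2 SD per week, or at slopes up to 0.4 if visits cluster with SD 0.6 weeks. At 0.3 SD per week with examinations spread over the whole window, it is about 5 points; at 0.5 it is 12 to 16, depending on what the planning SDs contain. All of this rests on assumed slopes and spreads.

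Two stronger readings should be avoided. The window is not shown to bias the result. Nor should a fall from 0.80 to 0.57 be charged to it: the first ten points come from a sample size that reaches 80% power only one-sided.

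**What to change.** - Record the date of each NNNS examination, derive exact PMA from it, and report its distribution by arm.
- For the approximately continuous NNNS scores, pre-specify a linear model of arm, randomisation stratum and PMA at examination (continuous), in place of the logistic model.
- Keep two sensitivity analyses: the unadjusted comparison, and a model with strata only.
- For floor-limited, skewed scores such as Hypertonicity, Hypotonicity and Handling, keep a rank-based comparison, for example stratified by randomisation stratum.
- Fix this before the codes are broken, since adding age later would look selective.

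The cost is one derived variable and some analysis text, with no extra visits or infants. The downside is that PMA at examination is measured after randomisation. If treatment shifted visit timing, adjusting for it would not be automatically unbiased. Check that it does not differ by arm; if it does, give weight to the strata-only model.

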 - o potentially life-threatening congenital anomaly
 - o known hereditary metabolic disorder
 - o known chromosomal abnormality
 - teratogen exposure with symptomatic substance withdrawal
 - o congenital viral infections
 - microcephaly
 - Grade IV intraventricular hemorrhage (IVH) or seizures documented within first 72 hours of birth
 - Critically-ill with life expectancy less than 72 hours
 - Unable to obtain consent within 72 hours of birth
 - Enrolled in another intervention trial

Participant recruitment: Parents or guardians of infants who meet study criteria will be approached regarding the study as early as possible within 72 hours of the infant's birth. Informed consent will be obtained by study investigators and coordinators. Permission will be requested to re-contact the families after completion of the supplementation study for follow-up.

Randomization: As previously described by Pande et al., enrolled patients will be randomized to either the treatment group (L-carnitine, 50 µmol/kg/day) or placebo group (5% glucose, similar volume as the L-carnitine group).²⁸ Patients who meet study entry criteria and have signed informed parental/guardian consent will be enrolled in the study. Because gestational age and small for gestational age (SGA) status will impact our outcome measures, we will ensure they are equally distributed in the arms of the study by stratifying based upon these variables. We will analyze the two study arms using an intent-to-treat analysis. Therefore, enrolled patients will be stratified into fourgroups: gestational age 23 to 26 6/7 weeks, gestational age 27 to 29 6/7weeks, gestational age 30 to 31 6/7 weeks and small for gestational age (SGA). Patients within each stratum will be randomized by the pharmacist using a computerized block-generation with sets of 4. In the case of multiple births, all infants must meet study criteria, and the infants will be randomized as a set. One infant of the multiple-birth set will be randomly chosen for inclusion in the analysis. A recruitment log of all screened infants will be maintained. Clinicians and the nursing staff will be unaware of the arm of the treatment protocol to which the patient is assigned. Codes will be unblinded only after all patients have reached the study end-point, or at the request of the Data Safety Monitoring Board.

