These measurements will be obtained through brain MRIs routinely obtained in preterm infants prior to discharge. There will be no change in the routine protocol in order to obtain these outcomes. The reading and analyses of these MRIs will be performed at no additional cost to the study subject.

Neurobehavioral Assessment:

Infants discharged from the Weiler and Montefiore North Division NICUs routinely follow-up with our neonatologists at term-equivalent age. At this visit, the infants routinely receive a neurobehavioral

assessment. We have chosen to administer the NICU Network Neurobehavioral Scale due to its prevalence of use in neonatal research and its strong psychometric properties.⁴⁹

The NICU Network Neurobehavioral Scale (NNNS) was developed by [name]., & [name].⁵⁰ The scale is intended for use with use with healthy and at-risk preterm infants and full term infants at risk because of prenatal substance exposure or other conditions. The NNNS can be utilized in either a clinical or research setting in order to obtain a comprehensive assessment of neurobehavioral functioning. There is a focus on neurologic, stress, and withdrawal signs. The tool may be used with infants through 6 weeks of age and may be used as early as 30 weeks for preterm infants. The exam assesses 115 items in three categories:

- Neurological items: active and passive muscle tone, primitive reflexes, and central nervous system integrity
- Behavioral state, sensory, and interactive responses
- Stress/abstinence items

The examiner assesses the items. Summary scores are generated for stress, withdrawal, and the major domains of neurobehavioral performance. The NNNS is administered in a standardized format which allows objective assessment of the infant. Normed scores are available for at-risk and healthy infants. Because the assessment is relatively new, there are no long-term studies looking at predictive validity. However, the test is based upon a variety of prior tools, where long-term predictive validity has been shown.⁵¹ The test takes approximately 20 minutes to administer. (Ordering information: http://www.brookespublishing.com/store/books/lester-7659/index.htm)

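### Prenatal substance exposure is recorded before treatment and bears on part of the NNNS, but the NNNS comparison is unadjusted; this costs a little precision and causes no bias

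*Combined protocol and SAP*

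**What the plan says.** - **Exclusion criteria (Methods/Design).** Exposure excludes only in the form "teratogen exposure with symptomatic substance withdrawal". This item has no time window of its own, but another exclusion is "Unable to obtain consent within 72 hours of birth", so eligibility is settled at about that point.
- **Data collection, maternal characteristics.** The form records "teratogen exposure (alcohol, tobacco or illicit drug use during pregnancy", which is fixed before randomisation.
- **Primary Outcomes.** The third is "Neurodevelopmental scores on the NICU Network Neurobehavioral Scale (NNNS) at 40 weeks post-menstrual age (+/- 2 weeks".
- **Neurobehavioral Assessment.** The NNNS is used "in order to obtain a comprehensive assessment of neurobehavioral functioning". The text adds "There is a focus on neurologic, stress, and withdrawal signs", and one of the three item groups covers stress and abstinence. The power table under Sample size lists 13 NNNS scores, including Stress Abstinence.
- **Outcome Measures (Statistical Analyses).** "Continuous data (percent weight loss, time to regain birthweight, NNNS score, BSID-III scores) will be compared" between arms by unpaired t-test, or by Wilcoxon's rank sum test for non-parametric parameters. The only adjusted analysis is logistic regression. Its named factors are gestational age, birth weight, race, gender and Apgar scores.
- **Elsewhere.** Exposure is not among the variables named under Baseline Comparability. The four randomisation strata are three gestational age bands and SGA.

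**The concern.** The protocol treats exposure as serious enough to exclude an infant once withdrawal is symptomatic. It then enrols exposed infants without symptoms and scores them on an examination that gives weight to withdrawal signs. If exposure moves any NNNS score in these infants, its effect sits in the error term of a primary comparison, although the variable that could remove it is already collected.

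The named logistic model does not fill the gap, because NNNS scores are analysed as continuous data. As written, no covariate clearly reaches the NNNS comparison. Exposure is also missing from the named baseline comparisons, so the plan does not ensure that an imbalance between arms would be seen. At stake is the precision of one primary outcome in a trial with about 50 analysed infants per arm.

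**Working it through.** **The plan's own figure.** Inputs from Sample size: 50 per arm, difference 0.5 SD, alpha 0.05, stated power 0.80. A one-sided t-test gives 0.799, so the stated figure reproduces. The two-tailed test set in Outcome Measures gives 0.697, and 0.80 would then need 64 per arm. That mismatch is a separate matter. Here 0.697 is simply the starting point.

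**Assumptions.** The documents give neither the share of exposed infants (p) nor the effect of exposure on a score (d, in SDs within exposure groups). I take p = 10-25% and d = 0.3-0.8.

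**Variance explained.** R² = p(1-p)d² / [1 + p(1-p)d²].
- Low end: 0.10 × 0.90 × 0.09 = 0.0081; R² = 0.0081/1.0081 = 0.008.
- High end: 0.25 × 0.75 × 0.64 = 0.12; R² = 0.12/1.12 = 0.107.

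**Power after adjustment.** The effective difference is 0.5/√(1-R²), entered in a two-sided t-test with 50 per arm.

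| p | d | R² | Effective difference | Power (unadjusted 0.697) |
|---|---|---|---|---|
| 10% | 0.3 | 0.008 | 0.502 | 0.700 |
| 10% | 0.5 | 0.022 | 0.506 | 0.706 |
| 25% | 0.5 | 0.045 | 0.512 | 0.717 |
| 25% | 0.8 | 0.107 | 0.529 | 0.745 |

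**The same variance seen as chance imbalance.** The 95% range of the difference in exposure between arms is 1.96 × √[2p(1-p)/50]: ±11.8 percentage points at p = 10% and ±17.0 at p = 25%. Multiplied by d and expressed in total SDs, this moves the arm difference by at most 0.035 (p = 10%, d = 0.3) to 0.128 (p = 25%, d = 0.8), against the 0.5 SD target. This is not a second harm. The standard error of the unadjusted test already contains it.

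**Bias.** In simulated unadjusted two-sided t-tests (40,000 trials per scenario, 50 per arm, no treatment effect), type I error was 0.051 (p = 10%, d = 0.5), 0.049 (20%, 1.0) and 0.048 (30%, 1.0). The mean difference was about zero each time.

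**Leaving exposed infants out.** At 10-25% exposed, 50 per arm becomes 50 × 0.90 = 45 to 50 × 0.75 = 37.5. Two-sided power at 0.5 SD is then 0.65 to 0.57.

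**The case against.** **The instrument.** A reader might infer that the NNNS is built to detect prenatal exposure. The protocol does not say so. It names as intended users "healthy and at-risk preterm infants and full term infants at risk because of prenatal substance exposure or other conditions", where the exposure phrase attaches to full-term infants, and this trial enrols only infants below 32 weeks. Nothing in the documents ties Excitability or Lethargy to exposure. This objection stands. The link that remains is the stated focus on withdrawal signs, most direct for Stress Abstinence.

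**Bias.** A reader might also infer that exposure distorts the carnitine estimate. Allocation is randomised and blinded, and the simulation shows no inflation of type I error. This stands too.

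**The size of the effect.** The examination is at 40 weeks ± 2, so an infant born before 32 weeks is examined at least about 6 weeks after birth (38 - 32). Infants with symptomatic withdrawal have already been removed, and the yes/no variable pools tobacco, alcohol and drugs. An effect of 0.8 SD is therefore a generous upper end. At 0.5 SD the gain is only about 1 to 2 points of power.

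**Why this covariate?** The NNNS comparison adjusts for nothing, not even gestational age. Other candidates, such as antenatal steroids and CRIB score, are recorded as well. The list of adjustment factors is open-ended, so exposure is unspecified rather than ruled out. It is fair to see this as one part of a wider gap, the absence of an adjusted model for continuous outcomes. An open list does not settle the point, however: it leaves the covariate to be chosen after results are seen, and the model it belongs to is logistic.

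**Conclusion.** The point holds as a minor one about analysis choice. A pre-randomisation variable, already on the case report form and plausibly related to at least one NNNS score, is not used in the NNNS comparison. The loss is precision only. Under the assumed 10-25% exposed and 0.3-0.8 SD effect, adjustment takes two-sided power from 0.697 to between 0.700 and 0.745. The upper figure needs both assumptions at their extremes, and at the low end the gain is close to nil. Both inputs are assumptions that the documents cannot confirm. The documents do not support a stronger conclusion, whether of bias, of an examination designed around exposure, or of a need to change who is enrolled.

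**What to change.** In Outcome Measures:

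1. For NNNS scores that are approximately continuous, prespecify a linear model with arm, randomisation stratum (gestational age group/SGA) and recorded prenatal exposure (yes/no for any of alcohol, tobacco or illicit drugs, with the definition fixed before unblinding).
2. Keep the plan's rank-based test for sparse or skewed scores. In the power table, Hypertonicity (mean 0.07, SD 0.26) and Hypotonicity (0.55, 0.76) are examples.
3. Under Baseline Comparability, report exposure by arm.
4. Keep all randomised infants in the primary analysis, subject to the plan's own rule for multiple births, and leave eligibility unchanged. An analysis without exposed infants is optional and descriptive only, given its power of about 0.65 to 0.57.

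The cost is a few lines of text and one degree of freedom for exposure. No new data are needed. Under-reporting by mothers would shrink the gain but would not favour either blinded arm.
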